#### 8.2 Determination of Sample Size and Accrual Rate

#### 8.2.1 Primary Endpoint

The primary endpoint of the study is the 12-month progression-free survival (PFS) with time counted from the CAR-T infusion conditional on being alive and progression-free at day +90 post CAR-T. An event will be defined as documented progression or death for any cause, subjects without an event will be censored at the last date known to be alive without progression. Left truncation at the time of the start of study treatment will be used to adjust for "immortal time" after day +90 before study enrollment.

#### **8.2.2 Primary Hypothesis**

We hypothesize that, with belantamab masodotin maintenance, the 12-month PFS conditional on being progression-free at day +90 will exceed 54%.

The comparison value was selected based on published and preliminary data from the KarMMa2 trial, with three-month PFS of 74%, and 12-month PFS of 40%, resulting in a conditional PFS of 0.4/0.74=0.54. A 5% one-sided type I error rate will be used.

#### **8.2.3** Sample Size Justification

The sample size was computed using 80% power at a one-sided 5% significance level to detect a significant effect if the conditional PFS exceeds the historical value by 20%, that is 74%. Assuming a 74% three-month PFS, this corresponds to a 12-month PFS of 55%.

The OptInterim R package was used to compute the optimal two-stage design that minimizes the expected sample size, assuming exponential PFS and recruitment of one patient/month during year 1, and two patients/months afterwards. The optimal design recruits a total of 45 subjects, with an interim analysis after 23 subjects have been enrolled, and followed for 12 months post-CAR-T. Recruitment will not be paused during for the interim analysis, and the information from all treated subjects (even those with incomplete

Short Title: MCW EMBRACE TRIAL Version No.: 3 Version Date: 12/29/2022 follow-up) will be used in the interim analysis. This design achieves an 84% power in the hypothesized setting, which exceeds the target due to the discreteness of the design space,

We conducted simulation studies to confirm that the actual study design maintains the target type I error and power under a range of scenarios, including non-exponential survival, up to 10% censoring, and an enrollment window of 1.5 months without additional adjustment of the sample size.

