#### 8 STATISTICAL CONSIDERATIONS

8.1 General Description

This phase II study will be conducted using an optimal two-stage design based on the methods of Huang (35). The enrollment target will be 45 subjects, with an interim analysis for futility after 23 patients have been enrolled, and followed for 12 months post diagnosis. Enrollment of new subjects will continue during that period.

The design is based on a modification of a binomial two-stage design that allows incorporation of data from subjects with less than full follow-up at the interim analysis (Huang, 2010). The study will enroll up to 45 subjects with an interim analysis performed when 23 patients have been treated and followed to the 12th month after CAR-T. The futility decision will use the Kaplan-Meier estimate of the 12-month progressionfree conditional survival using the data from the first 23 subjects and any subject who have been enrolled during the follow-up period of the 23rd subject. The study will be stopped for futility, if the one-sided ztest comparing the 12-month progression-free conditional survival to 54% defined by the null hypothesis has a p-value of 0.54 or higher. The study has a 70% probability of stopping for futility if the underlying 12-month conditional PFS equals to the null-hypothesis value of 54%.

If the study is not stopped for futility, study enrollment will continue until 45 subjects are enrolled. The final analysis will be performed when all subjects have been followed to 12 months after CAR-T. The Kaplan-Meier estimate of the 12-month progression-free conditional survival will be compared to 54% using a one-sided z-test at a 5% significance level.

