#### 8.3 Accrual Estimates

MCW is required (per MCW sIRB) to activate prior to other sites, whose activation times will vary due to internal activation timelines. Accrual is expected at one subjects/month during year 1, and two subjects/month afterwards. Therefore, enrollment is expected to last 29 months; last subject, last dose and assessment are expected to take another 11 months. Therefore, total trial duration would be approximately 40 months.

The study will reach study completion in approximately 10 years (five years for completion of treatment for all patients, and five years of long-term survival follow-up) from the time the study opens to accrual.

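### As worded, the futility look comes with 39–41 of 45 patients enrolled, so the interim trigger does not fit the claim that the design minimises expected sample size

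*Combined protocol and SAP*

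**What the plan says.** Section 8.2.3 says that the OptInterim package was used to find "the optimal two-stage design that minimizes the expected sample size", assuming exponential PFS and one patient per month in year 1, then two per month. The result is 45 patients in total, with an interim look after 23 have been enrolled and followed to 12 months after CAR-T, and a stated power of 84%. On accrual it says: "Recruitment will not be paused during for the interim analysis".

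Section 8.1 describes "an interim analysis performed when 23 patients have been treated and followed to the 12th month after CAR-T". Subjects enrolled while the 23rd is being followed also enter the interim estimate. The same section gives the trigger a second time as "followed for 12 months post diagnosis", which conflicts with the post-CAR-T wording. It stops for futility at a one-sided p-value of 0.54 or higher and gives a 70% chance of stopping under the null.

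Section 8.3 repeats the accrual assumption ("Accrual is expected at one subjects/month during year 1, and two subjects/month afterwards") and expects enrolment to last 29 months. No section says how many patients will be enrolled at the look, and none gives a value for the expected sample size.

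**The concern.** A two-stage design lowers expected sample size only if few patients have been enrolled when the stopping decision is made. Here the decision waits for full follow-up of 23 patients while accrual runs at its faster rate. If nearly everyone is enrolled by then, a stop saves almost no enrolment, and the expected sample size sits close to 45 whatever the stopping probability.

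At stake is the credibility of a stated design property, and what an ethics board or the DSMC believes the futility look can do. A mismatch between trigger and optimisation would also mean that the quoted stopping probability and power may belong to a look at a different time from the one that will be carried out.

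**Working it through.** **Inputs.** Accrual 1/month to month 12, then 2/month (8.2.3, 8.3). N = 45, trigger at 23 patients (8.1, 8.2.3). Treatment starts at day 90–120 after CAR-T, and enrolment is allowed from day 60 (3.1). Null 0.54 ("resulting in a conditional PFS of 0.4/0.74=0.54", 8.2.2), alternative 0.74 (8.2.3). Error rates: "A 5% one-sided type I error rate will be used" (8.2.2) and "The sample size was computed using 80% power at a one-sided 5% significance level" (8.2.3). Stopping probability under the null 70% (8.1).

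**Plan's own timeline.** Patient i > 12 enters at month 12 + (i − 12)/2. Patient 45 enters at 12 + 33/2 = 28.5, which agrees with the stated 29 months.

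**Time of the look.** Patient 23 enters at 12 + 11/2 = 17.5. If entry coincides with treatment start at day 90–120, month 12 after CAR-T is 8–9 months later, at month 25.5–26.5. Number enrolled by then: 12 + 2 × (13.5 to 14.5) = 39–41. If enrolment is at day 60, the lag is 10 months, the look is at month 27.5, and 12 + 2 × 15.5 = 43 are enrolled.

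**Expected sample size under the null.** E[N] = P(stop) × n at look + (1 − P(stop)) × 45.

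| n at look | P(stop) = 0.70 | P(stop) = 0.46 |
|---|---|---|
| 39 | 40.8 | 42.2 |
| 41 | 42.2 | 43.2 |
| 43 | 43.6 | 44.1 |
| 23 (look at 23rd enrolment) | 29.6 | 34.9 |

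The 0.46 column is there because, under the null, a one-sided p-value of 0.54 or higher occurs about 1 − 0.54 = 46% of the time (45–47% in simulation). A 70% stopping probability corresponds to p of about 0.30 or higher, or z at or below about 0.52; z at or below 0.54 gives about 70%.

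**Is about 41–42 a minimum?**
- Single-stage exact binomial, n = 39, reject at 27 or more: type I error 0.039, power 0.808. This is below the 40.8–42.2 expected under the two-stage rule.
- A grid search over N, look time and stopping probability, with accrual continuing, gives a minimum of about 25–28 for the plain Kaplan-Meier z-test (look at about 15–16 enrolled). On the log-cumulative-hazard scale the minimum is about 38 (look at about 24 enrolled).
- The single-stage comparison depends on scale: on the log-cumulative-hazard scale a single-stage design needs 47. The two-stage minimum of about 38 is still below 40.8.

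**Which look does the stated 84% power fit?** With 70% stopping, a normal approximation to the Kaplan-Meier z-test, with the final critical value set for 5% type I error, gives 80.1–83.3% for a look at month 17.5. For a look at month 25.5–26.5 it gives 88.1–91.9%. The range reflects null or alternative variance. The stated 84% is therefore closer to an earlier look, but on the log-cumulative-hazard scale no variant reaches 84% (70–79%). This is a hint, not proof.

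**Power cost of an earlier look.** Simulation, plain-scale Kaplan-Meier z-test, constant hazard over months 3–12, final test at z > 1.645, 6,000 trials per setting:

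| Look (month) | Enrolled | Power, z ≤ 0.54 | E[N] under null | Power, p ≥ 0.54 | E[N] under null |
|---|---|---|---|---|---|
| 17.5 | 23 | 78% | 30.1 | 87% | 35.1 |
| 20.5 | 29 | 84% | 33.8 | 90% | 37.8 |
| 26 | 40 | 89% | 41.5 | 90% | 42.7 |

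On the log-log scale with z ≤ 0.54, power is lower: about 73% at month 17.5 and 77% at month 20.5.

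**The case against.** The strongest reply is that continued accrual is disclosed, in both 8.1 and 8.2.3, and that giving up saved patients for a better-informed look is a legitimate choice. That stands: the late look is not an error in itself. It does not answer the optimality statement, which is a claim about expected sample size.

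Second, 39–41 rests on one of several accrual statements. The Protocol Summary expects about three years. Uniform accrual over 36 months (an assumption) is 45/36 = 1.25 per month, so patient 23 enters at month 18.4 and the look finds 33–34 enrolled, sparing 11–12; at 70% stopping E[N] is 36.6–37.3, below the single-stage 39. Section 3.3 says 24 months, which on the same uniform basis gives 38–39 enrolled. This also stands, but the design was optimised under the one-then-two-per-month assumption, and the claim has to hold there.

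Three stronger readings are tempting and not supported:
- A reader might infer that waiting for full follow-up throws away the method's use of incomplete data. It does not: at the look, 39 − 23 = 16 to 41 − 23 = 18 further patients contribute partial follow-up, which adds precision.
- A reader might infer that the plan promises minimal exposure to a drug with ocular toxicity and relies on this look to deliver it. Section 8.2.3 speaks only of expected sample size. Section 8.2.5 has separate toxicity monitoring every five patients, including a grade 4 corneal boundary. The 4–6 count covers future enrolees only; the plan does not say what a futility stop means for patients already on treatment.
- A reader might infer that the optimality claim is simply false and should be deleted. The software output is not in the document. If the optimised look was at or near the 23rd enrolment, the claim may be right and the trigger wording wrong.

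**Conclusion.** As worded, the trigger and the optimality statement do not fit together. Under the design's own accrual and a day 90–120 start, the look comes with 39–41 of 45 enrolled and E[N] under the null is about 41–42 (70% stopping) or 42–43 (about 45% stopping). That exceeds the recomputed minimum on every scale tried, and at 70% stopping it also exceeds an exact single-stage design of 39.

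The conclusion is limited to the stated optimality and to the small saving. Type I error and power are not damaged by looking late. The arithmetic on timing is firm given the accrual input. The comparison with a minimum rests on recomputed optima, since the plan gives no figure to reproduce, and the single-stage benchmark assumes complete 12-month follow-up and a binomial test. Which of the two statements is wrong cannot be settled from the document.

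**What to change.** Check the OptInterim output and reconcile the trigger with it:

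- (a) If the optimised look is earlier, for example at or shortly after the 23rd enrolment, rewrite the trigger in 8.1, 8.2.3 and the Protocol Summary as that calendar time or number enrolled.
- (b) If the look stays at 12 months' follow-up of 23 patients, remove the claim of minimum expected sample size.

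In both cases state the expected number enrolled at the look, E[N] under the null, and the stopping probability and power recomputed for that timing and for the corrected futility threshold (p ≥ 0.54 and 70% stopping cannot both be right). Replace "followed for 12 months post diagnosis" in 8.1 with the post-CAR-T wording.

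Cost: option (b) is a text change plus recomputed operating characteristics. Option (a) can cost power. Under the rule that gives about 70% stopping, moving the look from month 26 to month 20.5 costs about 5 points (89% to 84%). Moving it to month 17.5 costs about 10–12 points, to about 77–79%, below the 80% target and lower still on the log-log scale; N or the boundary might then need to change. Under p ≥ 0.54 as written the cost is about 0.5–2 points, nearer 3 at month 17.5 in the simulation tabulated above.

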#### 8.2.4 Analysis Populations

The overall study population will consist of all subjects enrolled into the study. This population will be used in study flowcharts and patient disposition summaries.

The efficacy population will consist of all enrolled subjects who received at least one dose of the study treatment and had at least one response evaluation after the start of the treatment. This population will be used for the primary efficacy.

The safety population will consist of all enrolled subjects who received at least one dose of the study treatment.

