#### 2.2 Primary Endpoint

1. Twelve-month conditional progression-free survival (PFS), defined as the probability of being alive without progression/relapse or death at 12 months from the time of CAR-T administration conditional on being alive without progression/relapse at 3 months from the time of CAR-T. Follow-up time will be counted from the date of CAR-T cell infusion, left-truncated at the start of study treatment, to the date of first documentation of progression or death due to any cause. Patients last known to be alive and progression-free are censored at date of last contact.

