For all subjects, disease evaluations will continue to be performed at least every 56 days (± seven days) until confirmed PD, death, start of a new anti-cancer treatment, withdrawal of consent, or loss to followup, whichever occurs first. Traditional efficacy assessment will be performed every cycle by serum protein electrophoresis and immunofixation and serum-free light chains, and after every two cycles by 24-hour urine protein electrophoresis and immunofixation. Minimal residual disease (MRD) assessment by next generation sequencing (clonoSEQ®), BCMA expression on bone marrow plasma cells and soluble BCMA/BAFF/APRIL will occur at screening and after two, six, and 12 cycles of belantamab mafodotin maintenance (refer to correlative schedule). In case of PD, subjects will be followed to ascertain subsequent anti-cancer therapy, if any, and survival status every six months (± 30 days) until withdrawal of consent, lost to follow-up, death, or the end of the study. Patients who discontinue treatment prior to progression will continue standard-of-care follow-up every three months until progression or start of another treatment (whichever comes first), then they will continue to long-term follow-up.

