#### 8.2.5 Statistical Analysis Plan

#### **Primary outcome**

PFS will be estimated by the Kaplan-Meier (KM) estimator, and presented with pointwise 90% confidence intervals. An event will be defined as documented progression or death for any cause, subjects without an event will be censored at the last date known to be alive without progression. Left truncation at the time of the start of study treatment will be used to adjust for "immortal time" before study enrollment.

The primary efficacy hypothesis of 12-month PFS exceeding 54% will be evaluated by comparing the KM-estimate to the null-hypothesis values using a one-sided z-test.

The primary outcome will also be summarized separately for subjects with ≤PR, and VGPR at the initiation of treatment. No between-group comparisons will be performed.

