#### Safety analyses

Safety analyses will be performed on the entire safety population. The incidence of severe adverse events will be reported for all subjects who received at least one dose of the study treatment. The proportion of patients experiencing an SAE will be reported overall, as well as classified by grade and organ system.

Formal toxicity monitoring will be performed for the following adverse events:

- SAEs that are possibly, probably or definitely related to treatment, with 30% acceptable rate
- Treatment-related grade 4 or higher non-hematologic toxicity, with 10% acceptable rate
- Grade 4 corneal adverse events, with 5% acceptable rate

Treatment-related death, i.e., grade 5 hematologic or non-hematologic toxicity, with 3% acceptable

The monitoring rules will suggest stopping the study when there is sufficient evidence that the proportion of patients with a specific adverse event exceeds the acceptable rate. Specifically, a Bayesian toxicity monitoring approach will be used, recommending stopping if the posterior probability of the event rate exceeding the acceptable rate is at least 80%. A Beta distributed prior with effective sample size of 1 and prior mean equal to the acceptable event rate was used for each event.

The tables assume that monitoring will be conducted after every five patients. Table 6 shows the cutoffs for the number of events that would trigger a stopping rule. For example, the third row shows that if 15 patients have been enrolled and 3 or more treatment-related non-hematologic AEs have occurred, then there is evidence to indicate that the proportion of these AEs exceeds the acceptable rate of 10%.

Table 6. Cutoffs for the number of patients with a specific adverse event indicating excessive rate of adverse event as a function of number of subjects in the study.

Subjects	Outcome			
	Treatment- related SAE (30%)	Treatment- related grade 4+ non-hematologic AE (10%)	Grade 4 corneal AE (5%)	Treatment- related death (3%)
5	≥ 3	≥ 2	≥ 2	≥ 1
10	≥ 5	≥ 3	≥ 2	≥ 2
15	≥ 7	≥ 3	≥ 2	≥ 2
20	≥ 8	≥ 4	≥ 3	≥ 2
25	≥ 10	≥ 5	≥3	≥ 2
30	≥ 12	≥ 5	≥ 3	≥ 3
35	≥ 13	≥ 6	≥ 4	≥ 3
40	≥ 15	≥ 6	≥ 4	≥3
45	≥ 17	≥ 7	≥ 4	≥3

Table 7 shows the operating characteristics of the boundaries listed in Table 6 for several values of true underlying probability of the adverse event. For example, if the true proportion of treatment-related SAEs is 40%, then the monitoring rule will be triggered over 83.6% of the time.

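### The primary efficacy population requires a post-dose response evaluation, so a treated patient who dies before one is a primary PFS event left out of the primary analysis

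*Combined protocol and SAP*

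**What the plan says.** Section 8.2.4 defines the efficacy population as enrolled subjects who received at least one dose "and had at least one response evaluation after the start of the treatment", and adds: "This population will be used for the primary efficacy". The safety population in the same section needs only one dose.

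The endpoint is defined without that condition. Section 2.2 has follow-up "left-truncated at the start of study treatment, to the date of first documentation of progression or death due to any cause". Section 8.2.1 says "An event will be defined as documented progression or death for any cause", and Section 8.2.5 (Primary outcome) repeats it. For patients with no event, Section 8.2.5 states that "subjects without an event will be censored at the last date known to be alive without progression".

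On timing, Section 3.1 says "disease evaluations will continue to be performed at least every 56 days", with serum efficacy tests once per 56-day cycle. In the study calendar (Table 1) the first myeloma assessment after dosing is at cycle 2 day 1. Section 4.7 says that treated subjects who later withdraw or are discontinued are not replaced.

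For the interim, Section 8.2.3 says that "the information from all treated subjects" will be used, including those with incomplete follow-up.

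**The concern.** The two definitions disagree about one kind of patient: someone who is dosed and dies before any response evaluation. Under Sections 2.2, 8.2.1 and 8.2.5 that patient is at risk from the first dose and has an event. Under Section 8.2.4 the patient is not in the analysis.

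The rule is selective. Progression normally has to be documented by an evaluation, so early progressors stay in. The exclusion falls mainly on early deaths, and removing them raises the estimate. Patients who leave alive and unevaluated are also dropped, although the plan's own rule would censor them; that loss has no fixed direction.

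The rule also works against the plan's method. Left truncation is there to remove immortal time before treatment. Requiring a later evaluation creates a new immortal interval after treatment starts.

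The estimate is compared with a fixed 54%, so no control arm shares the bias. The robustness simulations described in Section 8.2.3 cover non-exponential survival, censoring and the enrollment window, but do not list exclusions that depend on outcome. The same deaths would still count in overall survival and safety. The secondary PFS endpoint has no stated population, so only the primary test is certain to omit them.

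**Working it through.** **Inputs.** n = 45; interim when 23 subjects reach month 12, stopping if p ≥ 0.54; final one-sided 5% z-test against 54%; alternative 74% (Sections 8.1 to 8.2.3). Treatment starts at day 90 to 120 after CAR-T (Section 3.1). Accrual is one per month in year 1, then two (Section 8.2.3).

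**The plan's own figure.** Section 8.2.3 states 84% power. An exact binomial rule of at least 31 of 45 gives alpha 0.031 and power 0.830. A two-stage simulation with left truncation and a cumulative-hazard test using the null standard error gives power 0.83 and type I error 0.04 to 0.05. Power is 0.81 for a log-log test and 0.87 for an untransformed Greenwood test. The stated power is reproduced closely with all treated patients analysed.

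**Early events.** With exponential PFS under the null, the hazard is −ln(0.54)/9 = 0.0685 per month. The chance of a PFS event in the first 56 days (1.84 months) is 1 − exp(−0.0685 × 1.84) = 11.8%, or 0.118 × 45 = 5.3 patients. At 74% it is 6.0%, or 2.7 patients. The documents do not say how many of these would be unevaluated deaths, so that share has to be assumed.

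**Closed-form check.** Deleting k early deaths from complete data changes the expected estimate from 0.54 to 0.54 × 45/(45 − k). The last column is the rejection probability of a single-stage z-test with null variance.

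| k | Expected estimate | Nominal 5% test rejects |
|---|---|---|
| 0 | 54.0% | 5.0% |
| 1 | 24.3/44 = 55.2% | 6.9% |
| 2 | 24.3/43 = 56.5% | 9.3% |
| 3 | 24.3/42 = 57.9% | 12.4% |

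**Full design at a true 54%.** Let q be the assumed share of treated patients who die early and unevaluated. First dose is uniform over months 3 to 4, and the left-truncated Kaplan-Meier (KM) estimate uses Greenwood variance. There are 100,000 trials per row. The chance of at least one such death is 1 − (1 − q)^45.

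| q | At least one in 45 | Mean KM | Type I error, log-log | Type I error, untransformed |
|---|---|---|---|---|
| 0% | 0% | 0.5408 | 4.2% | 7.0% |
| 0.5% | 20% | 0.5444 | 4.7% | 7.7% |
| 1% | 36% | 0.5475 | 5.3% | 8.4% |
| 2% | 60% | 0.5545 | 6.7% | 9.9% |
| 3% | 75% | 0.5623 | 8.0% | 11.3% |

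The plan does not state the scale of the z-test, so both are shown. The 7.0% at q = 0 is the untransformed test's own excess and is not caused by this rule. A repeat simulation gave log-log values of 4.4%, 4.8%, 5.1%, 6.9% and 7.9%.

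**Exactly one deleted death.** The same simulated data were analysed with and without one early event (40,000 trials per case, restricted to trials that had one).

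| True 12-month conditional PFS | Mean rise in KM (points) | Negative to positive, log-log | Negative to positive, untransformed |
|---|---|---|---|
| 54% | 1.5 | 3.3% | 4.0% |
| 64% | 1.8 | 11.4% | 10.1% |
| 74% | 2.1 | 7.4% | 5.2% |

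The estimate fell in only 0.1% to 0.2% of trials, and changes from positive to negative were at most 0.02%.

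**A boundary case.** With complete data, 30 of 45 progression-free gives a log-log p of 0.054. Deleting one death makes it 30 of 44 and p = 0.0385. The untransformed test is already significant there (0.036 to 0.022); its own crossing is at 29 of 45 to 29 of 44 (0.072 to 0.048).

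**The case against.** The strongest reply is that such deaths will be rare. Patients must be progression-free, ECOG 0 to 2, with a life expectancy of at least six months and no recent infection needing treatment (Section 4.6). The two figures near 3% in the documents are poor guides to the first 56 days. One is a tolerance in Section 8.2.5: "Treatment-related death, i.e., grade 5 hematologic or non-hematologic toxicity, with 3% acceptable". The other is 3 of 95 fatal serious events (Section 1.4) at a different dose in patients with active disease. Both cover all treatment time. As an illustration, spreading 3% evenly over nine months gives 3% × 1.84/9 = 0.6% in the first 56 days. At 0.5% to 1% the log-log type I error is 4.7% to 5.3%, essentially nominal. The unstated test scale matters more: with no deletion, it alone moves type I error from 4.2% to 7.0%.

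That stands as a limit on the size, and the 2% to 3% rows should not drive the judgement. It does not remove the contradiction.

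Two further points also stand. Response evaluation is not defined, so an unscheduled paraprotein test or scan before death might keep a patient in; day 56 is the first scheduled evaluation, not the earliest possible one. And the interim wording in Section 8.2.3 may already include these patients, or may simply be loose. This matters little: keeping the deaths at the interim and deleting them only at the final analysis still gave log-log type I error of 5.3% at 1% and 7.7% at 3%.

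**Conclusion.** The concern holds. As written, Section 8.2.4 removes from the primary analysis a class of events that the endpoint definition counts, and no other section restores them. The bias almost always favours the drug. Its size depends on an unknown rate: none if no such death occurs, about 0.4 to 0.7 points on the mean estimate at 0.5% to 1%, and about 1.4 to 2.2 points at 2% to 3%. One deleted death can matter if the result is near the boundary. These sizes assume exponential PFS, uniform entry over months 3 to 4 and the futility cut as written. Confidence is high about the text and moderate about the magnitude. It should be corrected before outcome data are examined, because changing the population after an early death would be a data-driven choice.

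**What to change.** In Section 8.2.4, define the primary efficacy population, for both the interim and the final analysis, as all enrolled subjects who received at least one dose, at risk from the first dose. This is the existing safety population and agrees with the interim wording in Section 8.2.3. Count every death as an event. Censor living patients without an evaluation at the last date known alive and progression-free, as Sections 8.2.1 and 8.2.5 already provide. Keep the response-evaluable set for response summaries and as a sensitivity analysis of PFS, and define what counts as a response evaluation.

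The core change is one sentence. N stays at 45, the design's stated power is unaffected, and no new data are needed. The PFS estimate may be slightly less favourable.
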